6.4 Study Intervention Compliance

Not applicable.

6.5 Concomitant Therapy

All participants will be monitored throughout the study for use of concomitant medications. Any prescription medications including IVIG, blood products, over-the-counter (OTC) preparations, herbal remedies, and/or nutritional supplements taken during the study period must be recorded on the CRF.

It is also anticipated that participants may be treated with antibacterial agents, either for concomitant infection, or bacterial superinfection. The final decision for antibiotics (need, drug[s] and dose) and other medications will be made by the treating physician (except as noted below under Prohibited Medications).

6.5.1 Rescue Medicine

Not applicable.

7 STUDY INTERVENTION DISCONTINUATION AND PARTICIPANT DISCONTINUATION/WITHDRAWAL

Participants will be considered to have completed the study if they are followed through Study Day 60 (+ 90 days) and complete the final study visit (or followed through to death at or before 60 days).

7.1 Discontinuation of Study Intervention

Participants (or their legal surrogates if participants become unable to make informed decisions) can terminate study participation at any time without prejudice. If a participant terminates participation before completing the study, the reason for this decision will be recorded in the CRF. Participants who withdraw from the study will not be replaced.

Participants who indicate interest in withdrawing from the study should also be asked permission to be contacted at Day 29 and Day 60 (+90 days) by telephone for vital status (date of discharge, disposition, and any adverse events that occurred during the study). This is not considered full withdrawal of consent, but the modified consent for limited follow-up should be noted in the medical record.

Participants who fully withdraw consent will not be contacted further.

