7.2 Participant Discontinuation/Withdrawal from the Study

The investigator also has the right to withdraw participants from the study. Participants may be withdrawn from the study for either of the following reasons:

- The participant is lost to follow-up.
- The investigator believes that continuation in the study would be detrimental to the participant.

If appropriate, the participant should not be fully withdrawn but rather have limited further study interventions. This limited follow-up would entail contacting the participant on Day 29 by telephone for vital status (date of discharge, disposition, and any AEs that occurred during the study). The reason for withdrawal from the study is to be recorded on the CRF.

If a non-serious AE is unresolved at the time of discontinuation, efforts should be made to follow up until the event resolves or stabilizes, the participant is lost to follow-up, or there is some other resolution of the event. The investigator is to make every attempt to follow all SAEs to resolution.

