8.1.2 Measures of clinical support, limitations and infection control

On each study day while hospitalized through Study Day 29, the following measures for the previous day will be recorded. i.e., on Day 3, Day 2 measures are assessed as occurring anytime in that 24 hour period (00:00 to 23:59h):

- Hospitalization
- Oxygen requirement
- Non-invasive mechanical ventilation (via mask) requirement

- High flow oxygen requirement.
- Invasive mechanical ventilation (via endotracheal tube or tracheostomy tube) requirement.
- ECMO requirement.
- Ongoing medical care preventing hospital discharge (COVID-19 related or other medical conditions)
- Limitations of physical activity (self-assessed).
- Isolated for infection control purpose

If drawn for clinical care, record inflammatory markers, including:

- Ferritin, C Reactive Protein, D-Dimer, Fibrinogen, Erythrocyte Sedimentation Rate, Triglycerides, IL-6.

If and when a participant is discharged from the hospital, they will continue with study visits as an outpatient, for all Study Days that are applicable, including Days 15, 29, and 60. Outpatient visits will involve the participant returning to clinic, unless other reasonable accommodations for evaluations and blood draws can be arranged. Day 22 Study visit can be as a phone call. Given the COVID-19 restrictions and the difficulty some of the participants might have to attend an in person visit after hospital discharge, the collection of Day 60 data for primary and secondary endpoints and the collection of Day 60 samples for exploratory tests may be performed up to 90 days following the Day 60 visit. For these participants, the Day 60 data may be obtained from the information already entered in the clinical records by any clinician, or by contacting the participant by phone up to 90 days following the Day 60 visit to obtain retrospective data.

8.1.3 *Ordinal Scale*

The ordinal scale is an assessment of the clinical status at the first assessment of a given study day. From the measures collected in 8.1.2.1, this ordinal scale can be constructed.

The scale used in this study is as follows:

1. Not hospitalized, no limitations on activities.
2. Not hospitalized, limitation on activities and/or requiring home oxygen;
3. Hospitalized, not requiring supplemental oxygen - no longer requires ongoing medical care;
4. Hospitalized, not requiring supplemental oxygen - requiring ongoing medical care (COVID-19 related or otherwise);

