9.2 Sample Size Determination

A total of 80 participants are expected to enroll and be randomized in a 1:1 fashion to one of two study arms. Sample sizes are determined by desire to estimate safety and to provide a preliminary idea of efficacy. Given patients will be hospitalized at enrollment, we expect very low missing data rates for early safety and efficacy endpoints. We also expect to be able to have good follow-up post discharge until the end of the study. Patients will be analyzed for safety if they receive at least one dose of the experimental treatment. For efficacy endpoints, analyses will be according to the intent-to-treat principle and outcomes on all enrolled participants will be included for analysis. All power calculations assume Type I error rate of alpha=0.05. Power calculations were done using STATA/SE v16.0.

With a sample size of 40 for a given arm, the expected probability of observing zero or at least one adverse event at varying underlying adverse event rates under a binomial distribution is shown below in Table 3. At this sample size, it is likely to see at least one person with an adverse event even with relatively small rates of adverse reactions. For example, 40 individuals in one arm, there is an 80% chance of observing at least one individual with an event if the underlying AE rate is 4%. The analysis of AE rates will primarily be descriptive due to the lack of power to make formal comparisons with the control arm.

Table 3. Probability of detecting zero individuals or at least one individual with an Adverse Event (AE) for a variety of different underlying AE rates and sample size N =40

AE rate	Pr(0 events)	Pr(1+ event)
0.001	0.96	0.04
0.005	0.82	0.18
0.01	0.67	0.33
0.02	0.45	0.55
0.03	0.30	0.70
0.04	0.20	0.80
0.05	0.13	0.87
0.10	0.01	0.99

While the sample size is driven by safety considerations, we also consider the operating characteristics of the proposed sample size for the analysis of the primary and secondary efficacy endpoints. The primary efficacy outcome is a comparison of the clinical severity score. The severity score is based on

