The primary efficacy endpoint is the clinical severity score and will be calculated based on all randomized individuals (the intent-to-treat set). The key parameter of interest will be the comparison of clinical severity between individuals receiving the experimental intervention versus control, as measured by a clinical severity score that takes into account the survival time, recovery time, and Day 29 severity score for survivors who had not recovered by Day 29. Recovery is defined by time to reaching levels 1-3 in the 8-point ordinal scale. The severity score for the primary efficacy endpoint is calculated based on a procedure proposed by Shaw and Fay 2016 [21], which ranks all survivors better than non-survivors, individuals with shorter recovery times as better, and individuals with shorter times to death as worse. Shaw and Fay 2016 showed this test statistic can be interpreted as a weighted average of the log-rank type test statistic for survival and the one for time to recovery amongst survivors. If there are participants who survive to Day 29 but have not yet recovered, their clinical severity will be determined by their Day 29 ordinal severity score, using time to reach that level to rank those who had the same Day 29 ordinal severity. It is anticipated that this analysis will have more power to detect differences than looking only at only an individual endpoint. Secondary endpoints will include a comparison of each of the individual endpoints: time to recovery and survival. Further details for the statistical analysis will be provided in the SAP

9.4.3 *Analysis of the Secondary Endpoint(s)*

Key secondary efficacy endpoints include survival and time to recovery and will generally be calculated using the intent-to-treat set. Kaplan-Meier survival curves will be calculated by arm and compared with a Peto-Peto generalized Wilcoxon test. In the event that deaths that occur, the cumulative incidence of recovery will be estimated and compared between groups using Gray's test, which will be able to capture a lower time to recovery due to either a slower event rate or a higher death rate. For interpretive purposes the cause specific hazard ratios for will also be calculated for each event type, survival and recovery, along with the Peto-Peto test. In the event of no deaths, time to recovery will be summarized with the Kaplan-Meier and compared using the Peto-Peto generalized Wilcoxon test.

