6 Any laboratory tests performed as part of routine clinical care within the specified visit window can be used for safety laboratory testing. Window during the study period is ±1 day.

7 In-person visits are preferred but recognizing quarantine and other factors may limit the participant's ability to return to the site for the visit. In this case, these visits may be conducted by phone and blood and OP can be coordinated remotely.

8 Phone call at Day 22 is to assess clinical status (ordinal scale), adverse events, readmission to a hospital, and mortality only.

9 Safety laboratory tests on Day 15 and 29 if still hospitalized or returns to the site for the visit or at home visit.

10 The collection of Day 60 data for primary and secondary endpoints and the collection of Day 60 samples for exploratory tests may be performed up to 90 days following the Day 60 visit.

12.2 Division of AIDS (DAIDS) Table for Grading the Severity of Adult and Pediatric Adverse Events, Corrected version 2.1 (July 2017)

[Division of AIDS \(DAIDS\) Table for Grading the Severity of Adult and Pediatric Adverse Events \(Corrected Version 2.1 - July 2017\)pdf](#)

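### The limited Day 29 contact for withdrawn participants omits the ordinal level and the recovery date, so those still in hospital and not known to have recovered cannot be ranked on the primary efficacy endpoint

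*Combined protocol and SAP*

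**What the plan says.** - **Limited follow-up.** Section 7.1 covers withdrawal by the participant. Permission is sought for contact at Day 29 and Day 60 "by telephone for vital status (date of discharge, disposition, and any adverse events that occurred during the study". Section 7.2 covers withdrawal by the investigator and describes "contacting the participant on Day 29 by telephone for vital status (date of discharge, disposition, and any AEs that occurred during the study". Neither list includes the ordinal level, respiratory support or a recovery date. People who withdraw consent fully are not contacted.
- **Primary ranking (9.1 and 9.4.2).** Survivors rank above deaths, earlier recovery is better and earlier death is worse. "Recovery is defined by time to reaching levels 1-3 in the 8-point ordinal scale". For survivors who have not recovered by Day 29, "their clinical severity will be determined by their Day 29 ordinal severity score, using time to reach that level".
- **Recovery in hospital (8.1.3).** Level 3 is "Hospitalized, not requiring supplemental oxygen - no longer requires ongoing medical care", so recovery can come before discharge.
- **Population and missing data.** Section 9.2 applies intent-to-treat to efficacy, so that "outcomes on all enrolled participants will be included for analysis". Section 9.4.1 makes complete-case analysis the default and leaves imputation as an unspecified option.
- **The plan's own telephone visit (12.1, footnote 8).** "Phone call at Day 22 is to assess clinical status (ordinal scale), adverse events, readmission to a hospital, and mortality only".
- **Record retrieval (8.1.2).** Retrospective use of clinical records is described for Day 60 data only.

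**The concern.** The contact falls on the day of the primary efficacy endpoint, yet its item list leaves out what that endpoint needs. A participant can agree to be reached at Day 29, be reached, and still contribute nothing to the primary comparison.

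The participants exposed to this are survivors with long hospital stays. Under the complete-case default they drop out, and the arm that loses them looks better than it was. The trial is open-label, so withdrawal could be related to arm. If it were, the intent-to-treat comparison would be biased by data that could have been collected.

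**Working it through.** **Step 1. What the listed items return at Day 29, for someone not known to have recovered before withdrawing**

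| True state at Day 29 | Possible levels | Can the primary rank be derived? |
|---|---|---|
| Dead | 8 | Yes, if the date of death is recorded with the fatal SAE |
| Discharged alive | 1 or 2 | Yes. The discharge date is the latest possible recovery date, and is too late if level 3 came first |
| Still in hospital | 3, 4, 5, 6 or 7 | No. One level counts as recovered, four are distinct non-recovered ranks, and no date is collected |

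Disposition is not defined. Even if it returns that the person is still hospitalized, levels 3 to 7 are not separated. A readmitted participant who never met recovery would fall in the last row. That should be rare, because discharge alive already places a person at level 1 or 2, and no stated rule lets readmission undo recovery. Anyone who recovered before withdrawing is covered by the daily record.

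**Step 2. The plan's own power figure**

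Inputs from 9.2: 40 per arm, event rates 0.50 and 0.80, alpha 0.05 (two-sided assumed), Pearson chi-squared.

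Power = Φ{[0.30√n − 1.96√(2 × 0.65 × 0.35)] / √(0.50 × 0.50 + 0.80 × 0.20)}

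n = 40: (1.897 − 1.322) / 0.640 = 0.898, giving 81.6%. This agrees with the stated value of about 80%.

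**Step 3. Size if some participants cannot be ranked**

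No withdrawal rate is given, so a and b unrankable participants per arm are assumptions. Of the 40 × 40 = 1,600 between-arm pairs, those touching an unrankable participant number 40(a + b) − ab. A participant known to be alive outranks every death, so with D deaths per arm the count falls to (40 − D)(a + b) − ab. For illustration D = 11, from the 28% upper mortality figure in 2.3.3 (0.28 × 40 = 11.2).

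| Unrankable per arm | Pairs touched | Undetermined after removing pairs with a death | Complete-case power, 0.50 vs 0.80 |
|---|---|---|---|
| 1 | 79 (4.9%) | 57 (3.6%) | 80.5% |
| 2 | 156 (9.8%) | 112 (7.0%) | 79.5% |
| 4 | 304 (19.0%) | 216 (13.5%) | 77.2% |

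The third column is still a ceiling. The daily record shows no recovery up to withdrawal, so anyone in the other arm who recovered before that day also outranks the unrankable participant.

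For the matched-pair win calculation in 9.2 (win probability 0.80), a two-sided exact binomial test gives 98.1% power with 40 pairs, consistent with the stated figure of over 80%. It stays at or above 95.8% with 39, 38 or 36 pairs. The effect on power is small throughout.

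**The case against.** The strongest reply is that the gap is narrow. It needs a participant who withdraws before recovery, accepts limited contact and is still in hospital at Day 29. Section 9.2 expects very low missing data for early endpoints, and 5.5.2 describes retention measures. A short call may also be a deliberate way to keep people in contact. The scope argument stands and sets the severity. It does not remove the gap, because footnote 8 shows that ordinal status can be asked by telephone.

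A second reply is that scoring details are deferred to a separate SAP that is not in the document reviewed, and that the consent pages were removed from it. Either might help, but no scoring rule can recover a level or date that was never collected.

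A reader might also infer more than the documents support:

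- **That every withdrawn participant loses the primary endpoint.** Step 1 shows otherwise.
- **That failing to separate level 1 from level 2 matters here.** The modified score treats levels 1-3 alike as recovered and ranks them by time.
- **That readmission goes uncollected.** The call asks for adverse events, inpatient hospitalization is an SAE criterion (8.4.2), and start and stop dates are recorded for reported events (8.4.3.1). Readmission for an adverse event is largely captured.
- **That a large share of comparisons is lost.** Assuming 2 unrankable on plasma and 4 on control gives 232 of 1,600 pairs (14.5%). That split has no basis in the documents, and the count ignores that a known survivor outranks every death. With 11 deaths per arm it is 29 × 6 − 8 = 166 pairs (10.4%).
- **That withdrawal will differ by arm.** The open-label design makes this possible; nothing in the documents shows it.

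**Conclusion.** The point holds within a limited scope. Followed as written, 7.1 and 7.2 leave the primary rank underivable for a participant who withdrew before recovery, accepted limited contact and is still in hospital at Day 29 (or readmitted without prior recovery). For one who reached level 3 after withdrawing and was then discharged, the recovery time is late rather than missing.

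The number affected is probably small, but the plan gives no withdrawal rate from which to estimate it. One unrankable participant per arm would leave at most 3.6% of pairs undetermined under the assumed 28% mortality, with power for 0.50 versus 0.80 at 80.5%. The reason to act is that these missing data are avoidable and fall on the sickest withdrawn survivors, under a complete-case default in an open-label intent-to-treat comparison. This is a cheap improvement of minor severity.

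**What to change.** In 7.1 and 7.2, add these items to the limited follow-up:

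- the ordinal level at Day 29 and the date it was reached;
- the date of first reaching levels 1-3;
- the date of death, if applicable.

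At withdrawal, also ask for permission to take the 8.1.2 measures from the medical record through Day 29, so that the rank of someone still in hospital does not depend on a telephone answer. State how a participant with only a discharge date is scored. Participants who fully withdraw consent remain uncontacted.

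The cost is a slightly longer call that is already planned and a sentence in the modified-consent note. Some participants may decline record access. Sample size, alpha and treatment are unchanged.

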7.2 Participant Discontinuation/Withdrawal from the Study

The investigator also has the right to withdraw participants from the study. Participants may be withdrawn from the study for either of the following reasons:

- The participant is lost to follow-up.
- The investigator believes that continuation in the study would be detrimental to the participant.

If appropriate, the participant should not be fully withdrawn but rather have limited further study interventions. This limited follow-up would entail contacting the participant on Day 29 by telephone for vital status (date of discharge, disposition, and any AEs that occurred during the study). The reason for withdrawal from the study is to be recorded on the CRF.

If a non-serious AE is unresolved at the time of discontinuation, efforts should be made to follow up until the event resolves or stabilizes, the participant is lost to follow-up, or there is some other resolution of the event. The investigator is to make every attempt to follow all SAEs to resolution.

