
Compare the safety of plasma plus standard care vs. standard care alone by cumulative incidence of serious adverse events by day 60
	
 SAEs

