4. Expectedness to study treatment or process – [Unexpected – if the event severity and/or frequency is not described in the investigator brochure (if applicable) or protocol].
5. Action taken with respect to study or investigational treatment or process (none, dose adjusted, temporarily interrupted, permanently discontinued, unknown, not applicable)
6. Whether medication or therapy taken (no concomitant medication/non-drug therapy, concomitant medication/non-drug therapy)
7. Whether the event is serious

Once an adverse event is detected, it should be followed until its resolution or until it is judged to be permanent, and assessment should be made at each visit (or more frequently, if necessary) of any changes in severity, the suspected relationship to the study treatment, the interventions required to treat it, and the outcome.

For this study, all Grade 3 and 4 AEs, all SAEs occurring from the time the informed consent is signed through the Day 60 visit will be documented, recorded, assessed, and reported. In addition, any grade 1 or 2 or higher hypersensitivity reaction is also reported as an AE.

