9.4.4 Safety Analyses

The primary outcome is summaries by arm of the cumulative incidence of SAE, as described in [Section 8.4.2](#). Safety endpoints include death through Day 29, SAEs, discontinuation of study drug infusions, and Grade 3 and 4 AEs. Safety events will be analyzed as individual events and as part of a composite endpoint (e.g. any SAE). Proportions at specific study time points and by arm, e.g. Day 15, 22, 29 and 60, will be tabulated, as well as a Kaplan-Meier curve for death and time to first event for the composite endpoint. Each AE will be counted once for a given participant and graded by severity and relationship to COVID-19 or study intervention. AEs will be coded using the current version of the Medical Dictionary for Regulatory Activities (MedDRA). AEs will be presented by system organ class, duration (in days), start- and stop-date. Adverse events leading to premature discontinuation from the study intervention and serious treatment-emergent AEs will be summarized. Analyses will be primarily descriptive.

Events that would result in immediate study pause for DSMB review and the potential stopping of the study include: transfusion reactions or coagulopathic events. Plasma transfusion is a safe and commonly used treatment and so we do not anticipate additional SAE, above what these critically ill patients would experience as part of their baseline risk.

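### Section 7.2 provides only a Day 29 contact for investigator-withdrawn participants, which does not fit section 7.1 or the Day 60 safety follow-up required elsewhere in the protocol

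*Combined protocol and SAP*

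**What the plan says.** Section 7.1 deals with participants who want to leave the study. They "should also be asked permission to be contacted at Day 29 and Day 60 (+90 days) by telephone for vital status", and the content sought is discharge date, disposition and adverse events. Those who fully withdraw consent are not contacted again.

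Section 7.2 deals with withdrawal by the investigator, for either of two reasons: loss to follow-up, or "The investigator believes that continuation in the study would be detrimental to the participant". It then softens the withdrawal: "If appropriate, the participant should not be fully withdrawn but rather have limited further study interventions". The reduced schedule is a single contact: "This limited follow-up would entail contacting the participant on Day 29 by telephone for vital status". The content is the same as in section 7.1, but there is no Day 60 contact. The section ends with an instruction on events: "The investigator is to make every attempt to follow all SAEs to resolution".

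Three other parts of the protocol rely on information to Day 60:

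- Section 4.1 plans follow-up to Study Day 60 for every participant.
- Section 8.4.4 states that "all SAEs occurring from the time the informed consent is signed through the Day 60 visit will be documented, recorded, assessed, and reported", with no exception for withdrawn participants.
- Two analyses use the data. Section 3.3 lists a comparison of the arms on "cumulative incidence of serious adverse events by day 60", and section 9.4.4 states: "Proportions at specific study time points and by arm, e.g. Day 15, 22, 29 and 60, will be tabulated".

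**The concern.** Two adjacent sections set different limited follow-up for two kinds of withdrawal, and the protocol gives no reason for the difference. A coordinator who follows section 7.2 as written makes the Day 29 call and stops. The same coordinator has then made no contact that would reveal a new event between Day 29 and Day 60, although section 8.4.4 requires such events to be recorded.

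At stake is the completeness of the Day 60 safety data. Section 9.4.1 makes complete-case analysis the default, so a participant with unknown status after Day 29 could drop out of the Day 60 summaries. With 40 participants per arm, each one carries 2.5 percentage points.

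**Working it through.** The protocol states no figure on this point, so there is none to reproduce. The check is a comparison of the text, followed by an illustration of size.

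**Step 1. The sections side by side.**

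| Section | Who | Follow-up stated |
|---|---|---|
| 7.1 | Self-withdrawing, permission given | Telephone at Day 29 and Day 60 (+90 days) |
| 7.1 | Full withdrawal of consent | None |
| 7.2 | Investigator-withdrawn, where judged appropriate | Telephone at Day 29 |
| 4.1 | All participants | Through Day 60 |
| 8.4.4 | All participants | SAEs from consent through the Day 60 visit |

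The third row does not fit the last two.

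**Step 2. Does other text supply the missing contact?**

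- Following SAEs to resolution (section 7.2) applies to events already known. It does not find new ones.
- Section 8.1.2 allows Day 60 data to come from clinical records or a later telephone call. It is written for participants who have difficulty attending in person and does not mention withdrawn participants.
- Section 8.4.4 sets the obligation to record SAEs but gives no contact for this group.

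The obligation therefore exists, but section 7.2 gives no procedure to meet it after Day 29.

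**Step 3. Which results are exposed?**

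- Not exposed: the primary safety and efficacy endpoints (Day 29, section 3.1), 14- and 28-day mortality (section 3.2), and death through Day 29 (section 9.4.4).
- Exposed: the Day 60 SAE comparison (section 3.3, exploratory) and the Day 60 safety tabulation (section 9.4.4).
- Possibly exposed: survival time (section 3.2), for which no horizon is stated. It is affected only if analysed beyond Day 29.

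**Step 4. Size.** Inputs are n = 40 per arm (80 randomized 1:1, section 9.2) and k investigator-withdrawn participants per arm with unknown status from Day 29 to Day 60. The protocol does not give k; I assume 1 to 3.

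The endpoint is the proportion with at least one SAE (section 9.1), so anyone with an SAE by Day 29 is already counted at Day 60. Let m of the k be in that position. The best case counts none of the other k − m as events and the worst case counts all of them, so

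width of range = (k − m) / n.

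- m = 0, k = 1: 1/40 = 2.5 percentage points.
- m = 0, k = 2: 2/40 = 5.0 points.
- m = 0, k = 3: 3/40 = 7.5 points.
- m = 2, k = 3: 1/40 = 2.5 points.

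The figures with m = 0 are upper bounds.

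**Step 5. Chance that at least one first SAE goes unseen.** Assume a risk h of 5% to 20% of a first SAE between Day 29 and Day 60, independent between participants who were SAE-free at Day 29 (h is also not in the protocol). The chance is 1 − (1 − h)^k.

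- k = 1: 5% to 20%.
- k = 3: 1 − 0.95³ = 14.3% to 1 − 0.80³ = 48.8%.

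**The case against.** The strongest reply is that section 7.2 should not be read alone. Sections 4.1 and 8.4.4 make no exception for withdrawn participants, section 8.4.5.1 has adverse events reported until study completion, known SAEs are followed to resolution, and chart review is described in section 8.1.2. A site reading the whole protocol could well obtain the Day 60 information. This stands to the extent that a reader might infer the Day 60 data are lost, and the documents do not show that. They show an unresolved inconsistency and a risk that new events are missed.

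A reader might also infer that the missing data fall, by rule, on the participants most likely to have events, or that they will differ by arm. The documents do not support either inference. One of the two reasons in section 7.2 is loss to follow-up, where the data are missing for a cause other than this rule. For the other reason, plasma is given only on Study Day 1 and what follows is assessment and sampling, so a judgement that staying in the study is detrimental need not mark poor prognosis. The limited follow-up also applies only where judged appropriate. Open-label conduct makes a difference between arms possible, but nothing in the documents establishes one.

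The contrast with section 7.1 also has limits: self-withdrawing participants are asked for permission, so a Day 60 contact is not assured for them either.

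Finally, the Day 60 SAE comparison is exploratory and the adverse event analysis is mainly descriptive. That keeps the point minor, but it does not remove the inconsistency.

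**Conclusion.** The point holds as an inconsistency in follow-up with a modest consequence. Section 7.2 omits the Day 60 contact that section 7.1 seeks, and it does not fit sections 4.1 and 8.4.4. Read literally, it may leave new SAEs or deaths after Day 29 unrecorded for investigator-withdrawn participants who could still be contacted.

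The size rests on an assumed number of withdrawals. With 1 to 3 per arm, the Day 60 SAE proportion in that arm has a best/worst-case range of at most 2.5 to 7.5 points. That maximum applies only if all of them were SAE-free at Day 29 and nothing is learned about them afterwards. It is a bound and should not be read as an expected bias. A reader might extend the concern to the trial's main conclusions, but both primary endpoints are set at Day 29 and do not depend on the missing contact.

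**What to change.** Amend section 7.2 so that investigator-withdrawn participants who have not fully withdrawn consent have vital status, disposition and adverse events collected at Day 29 and at Day 60 (+90 days), by telephone or record review. This brings it into line with sections 7.1, 4.1 and 8.4.4. The change concerns data collection only.

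The cost is one further call or chart check per withdrawn participant, using wording already in section 7.1. It is a cheap improvement.
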